10.3. Tertiary/exploratory outcome measures

10.3.1 Neuroimaging:

1. Progression of Fe accumulation in deep gray matter structures of the brain as assessed by quantification of hypointense signal on T2* MRI imaging
2. Progression of retinal nerve fiber thinning as detected by OCT

10.3.2 Clinical:

1. Progression in cognitive dysfunction as assessed by PASAT component of MSFC (comparing area under curve (AUC) between 1 year of pre-treatment baseline collected during IPPoMS trial and one year of idebenone therapy)
2. Progression in cognitive dysfunction as assessed by Symbol Digit Modality Test (comparing area under curve (AUC) between 1 year of pre-treatment baseline collected during IPPoMS trial and one year of idebenone therapy)
3. Progression of neurological dysfunction as assessed by finger and foot tapping (comparing area under curve (AUC) between 1 year of pre-treatment baseline collected during IPPoMS trial and one year of idebenone therapy)

11. STATISTICAL ANALYSIS

11.1 Data acquisition and processing

All clinical, neuroimaging volumetric and biomarker data will be collected sequentially and analyzed in a blinded fashion from coded samples. Data will be acquired prospectively and transcribed to the research database. For the majority of imaging biomarkers the analysis will be performed only after completion of baseline or treatment periods, because the images need to be co-registered to the first acquired image. For biomarker data that can be acquired from cryopreserved biological samples, baseline and treatment data points will be evaluated simultaneously, to limit effect of inter-assay variation. Every effort will be made to have single rater/investigator to acquire one type of quantifiable clinical, neuroimaging and biomarker data for the entire cohort. Statistical analysis will be done by NINDS statistician.

11.2 Statistical analyses of outcome measures

Descriptive methods will be used to analyze the safety data. Generally, for the analysis of efficacy data in IPPoMS-E protocol, we will utilize equivalent outcomes collected during IPPoMS trial.

For primary and secondary outcome measures, we will use identical statistical approach as utilized in IPPoMS trial: i.e. in order to utilize all collected data, we will calculate areas under curve (AUC) values for each outcome, normalized per 1 year of “therapy”. Thus, we will calculate AUC for three different “treatments”: pre-treatment baseline (B), placebo (PI) and for idebenone (I) treatment. We will compare intra-individual changes in AUC values by following linear mixed effect model:

$AUC_{\text{outcome}} = \text{treatment (B, PL, I)} + \text{group} + \text{interaction between treatment and group} + \text{covariates}$

where “group” refers to original “placebo” versus “idebenone” groups from IPPoMS trial and the random part is patient. While randomization is stratified for age and therefore, we are expecting that the placebo and active treatment groups will be well-matched for age, we will use Age and sex as covariates in the model if we detect any interaction.

In addition to analysis of primary and secondary outcomes, combining data collected during IPPoMS and IPPoMS-E studies will significantly enhance our ability to detect treatment-related changes in CSF biomarkers. Depending on how many subjects choose to participate in IPPoMS-E, the amount of paired (i.e. no treatment versus idebenone) CSF samples may theoretically increase up to 2 fold in comparison to IPPoMS trial. Therefore, the cohort of patients originally assigned to placebo can be utilized as “confirmatory” cohort for biomarker changes identified in the IPPoMS trial. This would effectively increase the power for detecting significant differences, as only those biomarkers found to be significantly changed during the IPPoMS trial would be tested in the IPPoMS-E trial, thus limiting the number of multiple comparisons that would need to be performed (and for which p values need to be properly adjusted). Again, the differences in selected CSF biomarkers between “no-treatment”, “placebo” and “idebenone” treatment would be analyzed using the same mixed effect model.

Finally, combining CSF data from IPPoMS with IPPoMS-E will provide two different longitudinal datasets: for patients originally randomized to placebo, we will have three CSF samples off therapy (Mo -1: baseline, Mo 12&24: placebo) and for patients originally randomized to idebenone, we will have three CSF samples (Mo12, 24 and 36). These longitudinal data will allow us to calculate “slope” of progression and compare these slopes between two different treatments using again linear mixed model:

$\text{Biomarker} = \text{time} + \text{treatment} + \text{interaction between time \& treatment} + \text{covariate}$

where “treatment” is either idebenone or no idebenone (i.e. pre-treatment baseline + placebo). The interaction between treatment and time will assess if the slopes for two treatments are parallel or not. It has been suggested that evaluating changes in the “slope” of progression may distinguish true ongoing neuroprotective effect from static “symptomatic” effect (*Machado, Murray et al. 1999; Ginsberg 2008*). In other words, under hypothetical scenario that idebenone may prove efficacious in PP-MS, its effect on disability may vary depending on the pathophysiology of the disease. There are two possible scenarios:

1. That idebenone enhances ATP production in neurons, soon after initiation of its dosing, and this enhances electrical conduction in demyelinated axons. The result would be improvement in neurological function. However, if enhancement of ATP production does not also lead to neuroprotection, then the “slope” of progression after initiation of idebenone therapy would be parallel to the “slope” of progression off therapy. In other words, the efficacy on the outcome would be “static” – resetting the baseline, but not changing the “slope” (Figure 3A).
2. That idebenone enhances ATP production in neurons, oligodendrocytes and astrocytes. This may, to some degree, protect all CNS cells from death. As death of neurons and oligodendrocytes continues on a progressive basis, a true neuroprotective drug will inhibit

the slope of the measured outcome (e.g. progression of disability or CNS tissue destruction) in comparison to no treatment. Such dynamic effect would lead to a greater absolute difference in the outcome with greater duration of therapy (Figure 3B). Finally, the drug may have both symptomatic and neuroprotective effects (Figure 3C).

[figure not shown]

Figure 3:
Possible effects on the outcome (e.g. disability) by static “symptomatic” versus true “neuroprotective” therapeutic

- A. Static “symptomatic” effect will “reset the baseline” but will not alter the slope of progression
- B. True neuroprotective drug will change the slope of progression, so its efficacy on the outcome (i.e. the absolute difference in comparison to no treatment condition) will increase with the duration of treatment
- C. Combination of static and dynamic effect on the outcome by therapeutic that has both symptomatic and neuroprotective effect

Based on this rationale, for CSF biomarkers of CNS tissue destruction (that may be changing in time), we will evaluate the slopes of the change between idebenone and no idebenone treatments.

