5. STUDY OBJECTIVES OR HYPOTHESES

5.1 Hypothesis

We hypothesize that idebenone, through its combined effect on facilitation of mitochondrial metabolism and limitation of oxygen radical-induced CNS damage, will inhibit CNS tissue destruction in PP-MS patients.

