5.2 Goals of the study

The primary goals are:

1. To extend long-term (36 months) data on the safety and tolerability of idebenone at 2250 mg/day in patients with PP-MS.
2. To extend CSF biomarker data by significantly expanding (up to 2 fold if all eligible patients proceed to IPPOMS-E) the matched “baseline” vs. “idebenone treatment” CSF samples, which will be analyzed for biomarkers of oxidative stress, mitochondrial function and CNS tissue integrity.
3. To extend efficacy data for idebenone on CNS tissue destruction as measured by quantitative imaging biomarkers and clinical/functional biomarkers in patients previously completing IPPoMS (Protocol Number 09-N-0197). For patients originally randomized to active drug, the idebenone longitudinal data will be extended for total of 3 years, for patients originally randomized to placebo, 3 year pre-treatment or placebo-treatment period will be compared to 1 year idebenone therapy period.

The secondary goals are:

1. To further investigate the mechanism of action of idebenone in PP-MS.
2. To better define biomarkers indicative of therapeutic effect of idebenone on mitochondrial dysfunction and on limiting oxidative damage in PP-MS patients.

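### The single idebenone level in the section 11.2 AUC model covers 36 planned months in one group and 12 in the other, with no time term, so its treatment-by-group term cannot be read as a difference in response

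*Combined protocol and SAP*

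**What the plan says.** Section 11.2 sets the approach for primary and secondary outcomes: "in order to utilize all collected data, we will calculate areas under curve (AUC) values for each outcome, normalized per 1 year of" therapy. It names three levels, "pre-treatment baseline (B), placebo (PI) and for idebenone (I) treatment". The fixed part is treatment, group (original randomized arm), their interaction, and age and sex if needed; "and the random part is patient". There is no term for time or for length of exposure.

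Section 5.2 gives the planned exposures. In the idebenone arm, "the idebenone longitudinal data will be extended for total of 3 years". In the placebo arm, the "3 year pre-treatment or placebo-treatment period will be compared to 1 year idebenone therapy period".

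Further on, section 11.2 separates a static effect (scenario 1) from a neuroprotective one (scenario 2), of which it says: "Such dynamic effect would lead to a greater absolute difference in the outcome with greater duration of therapy".

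Other sections describe the comparison differently:
- **10.2.2 and 10.3.2** compare one pre-treatment year with one year on idebenone, without saying which year applies to patients who have had three.
- **10.2.1** speaks of rates for each patient.
- **3.4** compares patient-specific slopes in ex-placebo patients.
- **11.2** has a separate time-by-treatment slope model, for CSF biomarkers only. It also plans to use the ex-placebo patients as a confirmatory cohort, again for CSF biomarkers only.

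**The concern.** Dividing an AUC by its length makes periods of unequal length comparable when the level is constant within each period. It does not do so when the outcome drifts or the drug effect builds up. Here both are expected: PP-MS progresses, and scenario 2 is an effect that accumulates. Exposure length is fully tied to original group, and so is the study time at which level I is observed. The treatment-by-group term absorbs both.

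At stake is the reading of that term and of the I coefficient. A non-zero interaction could be taken to mean that early and late starters respond differently when all respond alike. If the interaction is dropped, I averages two exposures and corresponds to neither. In the CSF confirmation, a real effect could look smaller, or unconfirmed, because the confirming cohort has had less drug.

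**Working it through.** The documents give no effect size, SD, alpha or power for this study (section 11.4), so there is no stated figure to reproduce except the three years on idebenone: 24 + 12 = 36 months. Results are therefore in symbols.

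**Inputs.** Visits are every 6 months (7.4). B is Months −12 to 0 (10.2.2), placebo Months 0 to 24, and level I Months 24 to 36 (ex-placebo) or 0 to 36 (ex-idebenone) (5.2, 11.2).

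**Assumptions.** Change is linear, the drug effect is the same in everyone, and dosing is continuous:

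outcome(t) = a + βt + δ × (years on idebenone), t in years from Month 0.

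For a drug that slows progression, δ has the opposite sign to β.

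**Per-year AUC.** For a linear outcome the trapezoid is exact and equals the value at mid-period. Leaving out a:

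| Period | Mid-time (y) | β part | δ part |
|---|---|---|---|
| B, both groups | −0.5 | −0.5β | 0 |
| Placebo, Months 0-24 | 1.0 | 1.0β | 0 |
| I, ex-placebo, Months 24-36 | 2.5 | 2.5β | 0.5δ |
| I, ex-idebenone, Months 0-36 | 1.5 | 1.5β | 1.5δ |

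A static effect s present throughout the period enters as s in both groups.

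**I minus B.**
- Ex-placebo: 2.5β + 0.5δ − (−0.5β) = 3β + 0.5δ
- Ex-idebenone: 1.5β + 1.5δ − (−0.5β) = 2β + 1.5δ
- Interaction (ex-idebenone minus ex-placebo): δ − β

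An inert drug (δ = 0) gives −β, a 50% slowing (δ = −0.5β) gives −1.5β, and full arrest (δ = −β) gives −2β. As a check, the 11.2 model was fitted to simulated data (33 per group, assumed SDs, 100 runs per setting). The mean interactions were −1.01 (β = 1, δ = 0), −1.48 (β = 1, δ = −0.5) and −0.53 (β = 0, δ = −0.5), against −1, −1.5 and −0.5 from the formula.

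**Other readings of the AUC.**
- Measured from each period's starting value, level I is 0.5(β + δ) against 1.5(β + δ), a gap of β + δ.
- If the single year in 10.2.2 is the extension year for everyone, the ex-idebenone δ part is 2.5δ. The interaction is (3β + 2.5δ) − (3β + 0.5δ) = 2δ.
- If it is the first year on drug, both groups carry 0.5δ. The ex-idebenone change is 0.5β + 0.5δ + 0.5β = β + 0.5δ, and the interaction is (β + 0.5δ) − (3β + 0.5δ) = −2β.

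**Slope per period.** The rate is β in B and β + δ on idebenone in both groups, so the interaction is 0.

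**CSF.** Samples are yearly, not AUCs. Ex-placebo patients have one on-drug sample, at Month 36, carrying 1.0δ. The parent-trial on-drug samples carry (1 + 2)/2 = 1.5δ if Months 12 and 24 are averaged, or 2.0δ at Month 24 alone. The ratio is 1.5 to 2.

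**The case against.** The 36-month pooling is a reading of 11.2. Sections 10.2.2 and 10.3.2 say one year, and 3.4 and 10.2.1 point to slopes or rates, which are free of the problem. This stands as far as it goes: part of the defect is that the sections disagree. It does not clear the plan. No section says which year is meant, and both candidate years leave a non-zero interaction. The slope model in 11.2 is restricted to CSF biomarkers. Age does not act as a time term if taken at entry, since it is then constant within a patient.

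A static effect (scenario 1) enters equally, and section 5.1 says only that idebenone "will inhibit CNS tissue destruction in PP-MS patients". A reader might infer that the hypothesis itself claims an effect growing with duration; that statement is found only in scenario 2.

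Three stronger inferences are tempting and also unsupported:
- **That the interaction measures the exposure difference alone.** On raw AUC it is δ − β, so it appears even with an inert drug.
- **That the ex-placebo cohort would fail to replicate because its effect is one third the size.** The factor of three belongs to AUC outcomes. Confirmation is planned only for CSF, where the factor is 1.5 to 2. No decision rule is attached to the interaction.
- **That a given percentage of trials would show a false group difference.** Any such percentage depends on an assumed δ, assumed SDs and an assumed 33 per group (66 expected completers, equal split). It is not a property of the plan.

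Section 7.6.1 stops the study for futility, so 12 and 36 months are planned maxima. That lowers the stakes, but the same section transfers the data for continued analysis, so the definition of level I still matters.

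**Conclusion.** The point holds for section 11.2 as written, under its natural reading that all idebenone time is pooled. A uniform effect on progression rate enters level I as 1.5δ in ex-idebenone and 0.5δ in ex-placebo patients. The treatment-by-group term is δ − β, so it cannot be interpreted as a difference in response. For the CSF confirmation the imbalance is 1.0δ against 1.5-2.0δ.

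The algebra rests on linear progression, a constant δ and planned exposures; it needs no assumed SD or sample size. The CSF range also assumes that the parent-trial finding comes from Month 24, or from Months 12 and 24 averaged. The parent plan, to which 11.2 defers, is not in the documents. This should be corrected before the combined data are analysed.

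**What to change.** **Preferred.** In 11.2, analyse primary, imaging and clinical outcomes with a mixed model on the visit data, containing time in study and years since first idebenone dose. A uniform rate effect is then δ in both groups. An added on-drug step would keep scenario 1 separate from scenario 2.

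**Alternative.** Use the within-patient slope per period, as section 3.4 already does. One caution: a static effect s that appears after the starting visit tilts the slope unequally. With 6-monthly visits, least squares gives 0.5s/0.5 = 1.0s per year over 12 months and 1.5s/7 ≈ 0.21s over 36 months.

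**If AUC is kept.** Split I by year since first dose (I1, I2, I3), compare or pool the groups on I1 only, report I2 and I3 as long-term extension, and include a time term. I1 matching without a time term gives an interaction of −2β. That is larger than δ − β in size for any slowing short of full arrest. To estimate time alongside a placebo level and an I1-by-group term, placebo must also be split by year: unsplit, there are 7 group-by-period cells for 8 parameters; split, there are 8 for 8.

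**CSF confirmation.** Compare the change over 12 months of exposure from each patient's last off-drug sample: baseline to Month 12 (ex-idebenone) and Month 24 to Month 36 (ex-placebo). If the baseline sample is at Month −1, the intervals are 13 and 12 months, a residual of β/12.

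**Reconcile** 3.4, 10.2.1, 10.2.2, 10.3.2 and 11.2 on slope or AUC, and on which year on drug is meant.

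**Cost.** SAP wording and a few model terms, with no new data. The matched contrast uses 12 of the 36 planned on-drug months in ex-idebenone patients, so its interval is wider.

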The measurement and collection of data will be performed as in the randomized trial. Quantitative neuroimaging measures of central nervous system (CNS: i.e. brain and spinal cord) tissue destruction and clinical and functional measures of neurological disability will be collected every 6-12 months. Additionally, biomarkers focusing on analysis of reactive oxygen species (ROS) and oxidative stress will be collected every 12 months. The primary outcome measure defined in the IPPoMS trial will be also utilized in IPPoMS-E. For patients originally randomized to placebo, patient-specific slopes of disease progression during 2 years of placebo therapy (as measured by primary and secondary outcomes) will be compared to patient-specific slopes of disease progression during 1 year of open label idebenone therapy. Combination of IPPoMS and IPPoMS-E trials will significantly expand paired “no therapy” vs. “idebenone therapy” CSF samples for biomarker studies. It will also provide (for the subgroup of subjects who were originally randomized to idebenone) longitudinal CSF samples on idebenone therapy (collected 2 years apart). This will allow calculations of intra-individual changes in CSF biomarkers on and off idebenone therapy, which may provide important insight into the mechanism of action of idebenone in PP-MS.

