The aim of the present study is extend the data on safety, efficacy and effects on CSF biomarkers of idebenone 2250mg/day (5x150mg tablets three times per day) in patients with PP-MS, over a period of 1 year. Considering the dynamics of improvements in neurological function observed in double blind placebo-controlled trial of idebenone in LHON (*Klopstock, Yu-Wai-Man et al. 2011*) and in FRDA (*Di Prospero, Baker et al. 2007*) we believe that if there was a meaningful therapeutic effect of idebenone in PP-MS, then one year of active therapy would provide sufficient time to observe a difference in the rate of accumulation of neurological disability as compared to the 3 years of natural history from the IPPoMS placebo arm. IPPoMS-E will also provide safety and efficacy data for an additional 1 year in patients randomized to idebenone in IPPoMS.

Furthermore, the IPPoMS-E study will significantly expand the amount of longitudinal CSF biomarker data for idebenone-exposed PP-MS subjects. In patients randomized originally to active drug, IPPoMS-E study will effectively provide three yearly CSF samples on idebenone therapy. Such longitudinal CSF biomarker data on active therapy can be then compared to longitudinal CSF

biomarker data off therapy (i.e. 3 yearly CSF samples in the original placebo arm) for mathematical modeling studies that may provide support for, or contest, a potential neuroprotective effect of idebenone in PP-MS (see section 11: Statistical analysis). Furthermore, the number of paired CSF samples before and after idebenone therapy may theoretically increase up to 100% (if all patients choose to continue in IPPoMS-E protocol), although we consider it likely that some patient will decline participation in IPPoMS-E. This expansion of paired baseline versus treatment CSF samples will effectively provide confirmatory cohort for validation of the changes induced by idebenone treatment that were defined in original IPPoMS trial (see section 11: Statistical analysis).

[figure not shown]

Figure 2: IPPoMS-E trial design

We believe that expansion of efficacy on clinical, imaging and biomarker data may be highly important for supporting or refuting presumed therapeutic equipoise of idebenone and placebo in PP-MS and for selecting the optimal patient population and optimal trial design for the confirmatory trial in case IPPoMS and IPPoMS-E trials indicate therapeutic efficacy.

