10. OUTCOME MEASURES

10.1 Primary outcome measure:

The IPPoMS trial has an adaptive design that will determine the primary outcome measure for the IPPoMS protocol based on pre-determined analysis of the quantitative clinical and neuroimaging secondary outcome measures in the first 30 subjects who finish 1 year of pre-treatment baseline. This analysis is expected to be concluded in the spring/summer of 2013. The primary outcome measure that comes out of the pre-determined analysis in the IPPoMS trial will be adopted as primary outcome measure in the IPPoMS-E trial.

10.2 Secondary outcome measures:

10.2.1 Neuroimaging outcomes:

1. Inhibition of individualized rates of development of brain atrophy: effect of idebenone on individualized rates of development of brain atrophy
2. Inhibition of individualized rates of development of brain gray matter atrophy: effect of idebenone on individualized rates of development of segmented gray matter atrophy
3. Inhibition of individualized rates of enlargement of ventricular volume: effect of idebenone on individualized rates of enlargement of segmented volume of 3rd ventricle
4. Inhibition of individualized rates of development of cervical SC atrophy: effect of idebenone on individualized rates of development of SC atrophy
5. Inhibition of individualized rates of neuroaxonal destruction as assessed by T1 relaxation time in the brain (ROI in normal appearing white matter and in deep gray matter): effect of idebenone on individualized rates of neuroaxonal destruction

6. Inhibition of individualized rates of neuroaxonal destruction as assessed by T1 relaxation time in the cervical spinal cord: effect of idebenone on individualized rates of neuroaxonal destruction
7. Inhibition of individualized changes in axonal integrity as assessed by axial diffusivity and of changes in myelin integrity as assessed by radial diffusivity on brain DTI imaging: effect of idebenone on individualized rates of neuroaxonal destruction

10.2.2 Clinical/functional outcomes:

1. Progression of lower extremity disability as assessed by 25 foot walk component of MSFC (comparing area under curve (AUC) between 1 year of pre-treatment baseline collected during IPPoMS trial and one year of idebenone therapy)

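### The section 11.2 AUC model has no time term, so an inert drug can produce an idebenone-minus-placebo difference whose size and sign depend on an AUC definition not given; the off-drug comparator also differs between sections

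*Combined protocol and SAP*

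**What the plan says.** **Model (11.2).** The plan says "we will use identical statistical approach as utilized in IPPoMS trial" and that "we will calculate areas under curve (AUC) values for each outcome, normalized per 1 year of" therapy. Each patient's B, PL and I values enter a linear mixed model with treatment, original group, their interaction and a random patient effect. Age and sex are the only covariates named, and they are conditional. The section does not say whether AUC is taken on the score itself or on change, or from which starting point. It names no contrast as the one of interest. A model with a time term follows in the same section, but it is written for CSF biomarkers only.

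**Off-drug comparator for ex-placebo patients.**
- Section 3.4: patient-specific "slopes of disease progression during 2 years of placebo therapy (as measured by primary and secondary outcomes) will be compared to" slopes in the open-label year.
- Section 4.7: "a difference in the rate of accumulation of neurological disability as compared to the 3 years of natural history from the IPPoMS placebo arm".
- Section 5.2: "3 year pre-treatment or placebo-treatment period will be compared to 1 year idebenone therapy period".
- Section 10.2.2, for each clinical outcome: "comparing area under curve (AUC) between 1 year of pre-treatment baseline collected during IPPoMS trial and one year of idebenone therapy".

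**Other relevant text.** For ex-idebenone patients, section 5.2 says "the idebenone longitudinal data will be extended for total of 3 years". Section 10.2.1 words its first six imaging outcomes as rates, for example "effect of idebenone on individualized rates of development of brain atrophy". Section 10.1 leaves the primary outcome to be adopted from the parent trial.

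**The concern.** In ex-placebo patients the treatment label and calendar order are the same thing: idebenone always comes last. PP-MS is described in section 4.1 as progressive from onset. A model of period averages without time therefore attributes to treatment whatever the disease does between periods. The periods also differ in length, so change accumulated within a period differs even at a constant rate of worsening. The interaction does not repair this. Ex-idebenone patients have no placebo period, so that cell is empty, and no untreated patients are followed over months 24-36.

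At stake is whether the extension's efficacy contrasts can be read at all. Section 7.6.1 reports no significant efficacy in the parent trial, so a nearly inert drug is the case that matters. In that case the placebo-to-idebenone contrast could suggest harm or benefit depending on an undefined summary measure.

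**Working it through.** **Inputs from the documents.** B lasts 1 year (10.2.2), PL 2 years (3.1), and the two together 3 years (6.2). I lasts 1 year (3.3) and starts from the month 24 values (7.4). Ex-idebenone patients reach 3 years on drug (5.2). Clinical and brain MRI data are six-monthly (11.3). The documents give no figure on this point to reproduce.

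**Assumptions.** The drug is inert and worsening is linear, y = a + bt, with t in years from month 0. The documents give no value for b. For scales that fall with disability, b is negative. Ex-placebo periods are B (-1 to 0), PL (0 to 2) and I (2 to 3).

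**Formulas.**
- Level AUC divided by length equals the mid-period value: B = a - 0.5b, PL = a + 1.0b, I = a + 2.5b. The three off-drug years together give a + 0.5b.
- Change from the start of a whole period of length T: (bT²/2)/T = bT/2. So B = 0.5b, PL = 1.0b, I = 0.5b, and the three off-drug years 1.5b. Dividing by T does not remove period length.
- Change over each one-year segment: 0.5b every year.

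| Contrast, inert drug | Level | Change, whole period | Change, one-year segments |
|---|---|---|---|
| I - PL, ex-placebo | 2.5b - 1.0b = +1.5b | 0.5b - 1.0b = -0.5b | 0 |
| I - B, ex-placebo (10.2.2) | 2.5b + 0.5b = +3.0b | 0.5b - 0.5b = 0 | 0 |
| I - three off-drug years | 2.5b - 0.5b = +2.0b | 0.5b - 1.5b = -1.0b | 0 |
| (I - B) ex-idebenone minus (PL - B) ex-placebo, I = months 0-36 | 2.0b - 1.5b = +0.5b | 1.0b - 0.5b = +0.5b | 0 |
| Same, I = months 0-24 | 0 | 0 | 0 |

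The level reading makes an inert drug look harmful in ex-placebo patients. The whole-period change reading makes it look beneficial.

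**Curvature.** Take y = b[s ± 0.05s²], with s in years from the start of the baseline year. I - PL becomes +1.1b to +1.9b (level), stays at -0.5b (whole-period change), and is ±0.075b for one-year segments. The between-group figure for months 0-36 becomes +0.37b to +0.63b under the first two readings.

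**Check on the model itself.** The 11.2 model was fitted to 200 simulated null data sets per definition. Assumed inputs were 33 per group (the 66 completers of section 11.5 split evenly), b = 1, and SDs of 2 (intercept), 0.5 (slope) and 0.5 (residual). Mean I - PL was +1.50 (level) and -0.49 (whole-period change), in line with the formulas. Nominal 5% tests rejected in 100% and 96.5% of data sets, but these rates depend on the assumed inputs. A t-test approximation over 15 or 33 patients per group, b of 0.25 to 1 and residual SD of 0.5 to 2 gives 13% to 100% (level) and 5% to 96% (whole-period change).

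**The case against.** The strongest reply is that I - PL is not a contrast the plan designates for AUC. Where section 10.2.2 names an AUC contrast it is baseline year against idebenone year. Those outcomes are worded as progression, which favours a change reading, and there the bias is 0. Section 3.4 compares placebo with idebenone through slopes and section 4.7 through rates; both give 0 under linear worsening. Scaling to one year of therapy can also be read as one-year segments, which again gives 0. The parent protocol, which is not available here, may settle the definition. The three comparators overlap, since the three off-drug years are the baseline year plus the two placebo years.

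Much of this stands. I - PL is estimable from the 11.2 model but not singled out by it. The +2.0b and -1.0b entries put AUC on a comparison that section 4.7 words as a rate and for which section 5.2 names no statistic, so they are illustrations. The whole-period change false-positive rate has a median of only about 12% over the assumed grid.

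What does not fall is that section 11.2 applies AUC to every outcome, gives neither the segment definition nor a contrast, and carries the section 3.4 promise of slopes through only for CSF biomarkers. An analyst following it could obtain any column of the table.

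**Conclusion.** The concern holds as a defect of specification that can bias results. As written, section 11.2 permits an ex-placebo I - PL of +1.5b or -0.5b from an inert drug, a between-group bias of +0.5b if ex-idebenone data run to month 36, and +3.0b for the section 10.2.2 contrast on the level reading. These sizes need only the period layout and linear worsening.

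A reader might infer that the trial's primary result is biased by these amounts. The documents do not support that: the primary outcome is not yet chosen, slopes and rates are unbiased under linearity, and so are the concurrent months 0-24 comparison and the one-year change contrast. A reader might also infer a false-positive rate near 100%. That rests on values of b and SDs that the documents do not give.

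It should be fixed, with low to moderate consequence. Section 7.6.1 stops the extension for futility but transfers its data to protocol 09-N-0032 for continued analysis.

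**What to change.** **Model.** In section 11.2, analyse the primary, clinical and imaging outcomes at visit level with a linear mixed model: time, time since first idebenone dose (0 before it) and original group, with random intercept and slope per patient. Name the coefficient of time since first dose, the change in yearly slope, as the contrast.

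**Comparator.** State one off-drug comparator identically in sections 3.4, 4.7, 5.2 and 10.2.2. Starting at month 0 gives the two placebo years of section 3.4; starting at the baseline year gives the three years of sections 4.7 and 5.2.

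**Step term.** Decide this per outcome, not per patient. Include an on-drug step for every outcome scheduled at two or more post-dose visits. Without a step, a purely static effect d appears in ex-placebo patients as a slope change of 1.0d per year (months 30 and 36) or d/0.5 = 2.0d (month 30 only). That confuses the symptomatic and neuroprotective effects section 11.2 sets out to separate. Where only one post-dose visit exists, report a combined static-plus-slope effect, not a slope change. This applies after early stopping at month 30 and to the spinal cord MRI in ex-placebo patients. That scan is placed at month 30 in section 7.5.3 and month 36 in Appendix A, which must be reconciled.

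**Checks that do not rely on linearity.** Report the concurrent months 0-24 comparison and a both-group model with visit as a factor.

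**If AUC is kept.** Define it as change from the start of equal one-year segments and drop the empty placebo-by-idebenone-group cell.

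**Cost.** Wording and programming, and a departure from the parent trial's approach. Two limits should be stated:
- *Linearity.* Under y = b[s + 0.05s²], an inert drug in ex-placebo patients gives a month 30-36 slope of 1.375b against a placebo slope of 1.2b, a bias of 0.175b (about 0.18b). Including the baseline year lowers the off-drug slope to 1.15b and raises the bias to 0.225b.
- *Precision.* With residual SD 0.5, b = 1 and 33 ex-placebo patients (assumed), the variance per patient with step is 2(0.25)/0.5² + 0.25/2.5 = 2.1. The SE is √(2.1/33) = 0.25b.
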